## 1. Introduction and Background

In the Children’s multimedia study, we propose to investigate the effects of media multi-tasking on child obesity. The modern obesogenic environment is replete with cues to eat. Environmental food cues stimulate brain reward regions and lead to excess consumption independent of hunger levels (1). This cued eating is partially mediated by the amount of attention given to food cues. For example, children who spend more time looking at food cues consume more calories than children who do not (2). We propose that the prevalent practice of media multi-tasking—simultaneously attending to multiple electronic media sources—increases attention to peripheral food cues and subsequent cued eating and thereby plays an important role in the development of obesity. Neural networks are responsible for controlling attention to peripheral cues. The dorsal and ventral orienting networks control the shifting and focusing of attention, and the frontoparietal network controls the filtering of peripheral cues in the environment (3-5). Media multi-tasking is known to increase orienting and decrease the filtering abilities associated with these networks (6-8). By this mechanism, we propose that media multi-tasking increases obesity risk by increasing attention to peripheral food cues. Current efforts to address obesity ignore this prevalent risk behavior. Fortunately, it is possible to improve the functioning of the attentional networks through attention modification training (9); thus this research examines the hypothesis that attention modification training can decrease the amount of attention children give to food cues.

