## Theoretical Model

We propose that the persistence of childhood obesity (Figure 1) is caused, in part, by the rise in media multi-tasking that alters attention to peripheral cues, rendering some children more susceptible to cued eating. We expect that high levels of media multi-tasking weakens the attentional network responsible for filtering out distracting environmental cues (frontoparietal network) and strengthens the attentional networks responsible for shifting and focusing attention to peripheral cues (ventral and dorsal orienting attentional networks) (3-5). We theorize that by altering these attentional networks, media multi-tasking renders children particularly susceptible to food cues, thereby leading to cued eating. The functioning of attentional networks can be modified through attentional training that improves sustain attention, which we expect can provide a protective effect against overeating by decreasing attention to food cues.

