## **Media multi-tasking may alter neural attentional networks and thereby increase attention to food cues and prompt greater consumption.**

Attention to peripheral food cues is controlled by a series of attentional networks. The frontoparietal attentional network is responsible for filtering distracting environmental cues, and the ventral and dorsal orienting attentional networks are responsible for shifting and focusing attention to peripheral cues (3-5). Research has shown that these networks undergo a critical developmental period during childhood in which changes that occur during this period often track into adulthood (11). Frequent media multi-tasking has been associated with increased attention to peripheral cues. This result was documented by Nass and colleagues who studied how an individual's self-report of light or heavy usual media multi-tasking related to their performance on well-established behavioral paradigms of attention (8). Neuroimaging studies have shown that media multi-tasking is associated with activity in brain areas of the frontoparietal attentional network (6), and our own pilot data has shown that high media multi-taskers have greater cue reactivity to extraneous food cues in known brain reward areas (C.1.2). Consistent with these findings, high media multi-taskers are known to have a greater spread of attention to peripheral cues (7). These studies are based on a well-established attentional network theory of attention (3-5) and provide converging behavioral and neuroimaging evidence that high media multi-taskers are particularly susceptible to the influence of peripheral cues. The cross-sectional nature of these past studies limits inference about the direction of causality between media multi-tasking and attention to peripheral cues. We will address this limitation in the literature through our controlled experimental design. In addition, no studies have considered the effects of media multi-tasking on attention to food cues and consumption. The effect of media multi-tasking on attention to environmental food cues, specifically, is warranted because some evidence suggests that food cues require different attentional demands than less salient cues (31-33). There is a potentially large significance in understanding how media multi-tasking affects attention to food cues given that attention to food cues has been robustly related to consumption in both adults and children in a number of studies that have used a variety of attention paradigms (2,34,35).

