
## 2. Objectives and Hypotheses

[figure not shown]
Our long-term goal is to understand the determinants of children’s individual susceptibility to environmental food cues and cued eating to develop interventions that reduce childhood obesity. Our overall objective is to determine how media multi-tasking affects attention to peripheral food cues and overeating, and whether it is possible to intervene on this proposed pathway. We have two central hypotheses. The first is that engaging in media multi-tasking increases attention to peripheral cues and thereby makes children more susceptible to environmental food cues (e.g., food advertising, sight or smell of food) that leads to cued eating in the absence of hunger. The second is that attentional training that improves sustained attention protects children against attention to peripheral food cues and therefore makes them less susceptible to cued eating.

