## APPROACH

### Main Study

We will achieve our aims by having 13-17-year-olds visit the laboratory on three occasions to complete each of three tasks: a media multi-tasking paradigm, an eye-tracking task that measures attention to food cues, and an EAH paradigm. Additionally, children will complete a questionnaire-based media multi-tasking scale. Children will be randomized to complete the multi-task, sustained attention, or control condition of the media multi-tasking paradigm during their first visit and will complete the alternate conditions during their second and third visits. The experimental flow for individual laboratory visits is shown in Figure 2.

**Preload meal.** In order to control for satiety, children will be fed a standardized palatable dinner at the beginning of the study using established methods (48).

**Multi-tasking experimental manipulation.** Immediately following dinner, children will complete one of three conditions (attentional training, acute media multitask, or control) in a modified version of the Go/No-go task to simulate media-multitasking.

**Attentional training.** A Go/No-go task was used to train sustained attention. For the task, a blue or yellow dot briefly appeared for between 20 - 1500 msec and then disappeared. Participants were instructed to respond to the blue dot by pressing the space bar as quickly as possible (Go trials) and were told not to respond when presented with a yellow dot (No-go trials). At random intervals between 2000 – 5000 msec the messaging bot would ding and send participants a text message. The text message included questions about random facts; for example, how many teeth does an alligator have? Participants were instructed to ignore the messages and focus on the Go/No-go task. By asking participants to practice ignoring incoming messages and focus on a task designed to increase sustained attention, the training condition was designed to reduce acute media multitasking and increase sustained attention. Participants completed 100 Go trials and 100 No-go trials randomized on a trial-to-trial basis. There was a total of 60 messages sent to participants.

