We assessed power to detect a significant correlation between each predictor and our outcome using Cohen's method for Pearson's correlation coefficient (74). Using 107 participants (assuming a retention rate of 85%), 80% power, and a Type I error rate of 0.05 (two-tailed), we calculated that Aim 1 is powered to detect a moderate effect size of  $|r \geq 0.27|$  for either predictor with EAH. Cross referencing this effect size and our power analysis parameters with the empirical power tables for mediation created by Fritz and Mackinnon (75), we found that that our study is 80% powered to detect if media multi-tasking fully mediates the relationship between attention to food cues and EAH.

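### The stated 80% mediation power is for the reverse of the hypothesised pathway, attaches to no planned indirect-effect test, and cannot be checked from the inputs given

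*Combined protocol and SAP*

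**What the plan says.** The last paragraph of section 4 (Analysis) takes 107 participants, a two-sided 5% level and 80% power, and arrives at a detectable correlation of 0.27 "for either predictor with EAH". It then looks that value up in published power tables for mediation and concludes that "our study is 80% powered to detect if media multi-tasking fully mediates the relationship between attention to food cues and EAH".

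The scientific sections describe the pathway in a different order:

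- Section 1, Introduction and Background: "we propose that media multi-tasking increases obesity risk by increasing attention to peripheral food cues".
- Theoretical Model: "media multi-tasking renders children particularly susceptible to food cues, thereby leading to cued eating".
- Background heading on attentional networks: "Media multi-tasking may alter neural attentional networks and thereby increase attention to food cues and prompt greater consumption".
- Section 2, first central hypothesis: "engaging in media multi-tasking increases attention to peripheral cues and thereby makes children more susceptible to environmental food cues".
- Section 2, second central hypothesis, on attentional training: it "protects children against attention to peripheral food cues and therefore makes them less susceptible to cued eating".

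On timing, the Main Study text says "Immediately following dinner, children will complete one of three conditions", and the eye-tracking game that measures attention comes straight after that task. Usual multi-tasking is a separate questionnaire score.

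The first part of section 4 names three primary outcomes (changes in first fixation, cumulative fixation and EAH) and two primary exposures (multi-task vs control, sustained attention vs control). It plans a regression linking change in attention with change in EAH, then tests usual multi-tasking as a moderator by a median split and a product term.

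**The concern.** In both central hypotheses, attention is what links multi-tasking or training to eating. The one sentence that gives power for a mediated effect puts multi-tasking in the middle instead, and no analysis in section 4 estimates a mediated effect in either direction.

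If an indirect effect is later reported, its model, interval method and attention metric will have been chosen without a plan. Section 4 offers four attention measures (two fixation durations and two food-bias versions) and two contrasts, so there are 4 × 2 = 8 candidate indirect effects on EAH. A reader could also attach to whichever is reported an 80% power that was stated for another pathway and rests on path sizes nobody can see.

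**Working it through.** **Step 1. Direction.** The power sentence reads attention → multi-tasking → EAH. Sections 1 and 2 and the Theoretical Model read multi-tasking (or training) → attention → eating. Two meanings of multi-tasking are possible in the power sentence:

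- *The assigned task.* It is allocated at random and done before attention is measured at that visit. Attention measured afterwards cannot cause it, so it cannot be the mediator.
- *The usual multi-tasking score.* Section 4 uses this score as a moderator. A mediator role appears nowhere else in the document.

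Neither meaning makes the sentence consistent with the rest of the plan.

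**Step 2. Matching analysis.** Condition vs control on change in attention bears on path a. The regression relating change in attention to change in EAH bears on path b. Section 4 gives no product of paths, joint rule, interval or test that combines them.

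**Step 3. Reproduce the figure that can be reproduced.** Inputs from section 4: r = 0.27, n = 107, two-sided 0.05. By Fisher z:

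power = Φ(atanh(0.27) × √(107 − 3) − 1.960) = Φ(0.2769 × 10.198 − 1.960) = Φ(0.864) = 0.806.

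The 80% for a single predictor-EAH correlation is therefore right.

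**Step 4. Try to carry 0.27 into a mediation model.** With standardised variables and no direct effect (full mediation), corr(X, Y) = a × b and corr(M, Y) = b. If both predictor-EAH correlations equal 0.27, then a = 0.27 / 0.27 = 1, meaning exposure and mediator are the same variable. So 0.27 cannot be both correlations at once, and the document does not say which path it stands for.

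**Step 5. Illustration.** *All path sizes here are assumptions.* Simulation of a single-level X → M → Y model, direct effect 0, n = 107, two-sided 0.05, standardised paths, 40,000 replicates for each joint-significance figure except 0.27 / 0.59 (20,000):

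| a (X→M) | b (M→Y given X) | Power, both paths significant |
|---|---|---|
| 0.27 | 0.27 | 63% |
| 0.31 | 0.31 | 79% |
| 0.32 | 0.32 | 82% |
| 0.27 | 0.59 | 81% |
| 0.40 | 0.675 (a × b = 0.27) | 99% |

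The first row can be checked by hand: path a alone has power 0.808 and path b alone 0.778, and 0.808 × 0.778 = 0.63.

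The choice of test matters as well. At a = b = 0.27 the Sobel test gives about 42%, a percentile bootstrap about 64% and a bias-corrected bootstrap about 74% (1,500 replicates for the bootstraps).

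**Step 6. Closer to the design.** The trial compares conditions within child. Assume a standardised mean change in attention of 0.27 and a change-on-change correlation of 0.27. A paired simulation at n = 107 then gives 63% for both being significant. The agreement with the first row is a coincidence of scale: a standardised mean change and a correlation are different quantities.

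**The case against.** The strongest reply is that two nouns were transposed in one sentence. The rest of the document agrees on the order, and swapping the labels leaves the power unchanged if the two path sizes stay the same. That is fair for direction alone. It does not supply the missing indirect-effect analysis, the path sizes or the test.

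A second reply is that section 4 already holds the ingredients of both paths, and a joint-significance rule needs no product term. This stands in part: what is missing is the rule that combines the pieces and the choice of metric, not the data or the component regressions.

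A third is that an effect size and a published source are given. That is also true, so this part is a reporting gap and not a contradiction. Only the direction is a contradiction. The Aims that the power text refers to are not defined in the text available, and figures are missing, but section 4 itself shows no gap.

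A reader might infer that true mediation power is below 80%. The documents do not support that: 63% follows only from assuming 0.27 for both paths, and other path sizes give 80% or more. Nor should very low values from between-person models with a large exposure-mediator path be used. They come from collinearity between exposure and mediator, which a paired within-child analysis does not have. For example, a paired run with an assumed standardised change of 0.9 and a correlation of 0.30 gives about 88%.

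**Conclusion.** The point holds and should be fixed. The 80% mediation power is stated for a pathway that the trial does not hypothesise and that section 4 does not test. It can be neither confirmed nor refuted, because 0.27 is not mapped to the two paths or to a test. The power for the single correlation is correct at 80.6%. Under the illustrative assumption of 0.27 on both paths at n = 107, joint-significance power is about 63% and Sobel about 42%; about 80% needs both paths near 0.31 to 0.32. These figures come from a between-person model and only show how far the answer depends on what is unstated.

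A reader might also infer that the main comparisons are compromised. They are not: the primary outcomes and exposures do not depend on this sentence.

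**What to change.** 1. In the power paragraph of section 4, name attention to food cues as the mediator of each condition-vs-control effect on EAH. If the usual multi-tasking score was meant, say so and reconcile it with its moderator role earlier in the section.
2. Withdraw the 80% mediation figure, or restate it for the within-child contrast with both path sizes and the test named.
3. So that the trial can address its central hypothesis, add to section 4 one secondary within-child indirect-effect analysis per contrast, with one attention metric named in advance. Path a is the mean within-child change in attention. Path b is the slope of change in EAH on change in attention, allowing for visit order. Report a × b with a bootstrap interval that resamples children.
4. State that path b is observational, since attention is not randomised. The task and scoring descriptions are partly in the past tense, so label the analysis post hoc if outcome data have already been examined.

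Items 1 and 2 cure the inconsistency on their own; item 3 is what makes a mediation claim possible. The cost is a few sentences, one small extra analysis, and a power figure that is withdrawn or becomes conditional. No participants, visits or measurements are added.

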#### 5. Study Progress Monitoring

Note: appropriate monitoring may include periodic assessment of the following:

- data quality
- timelines
- recruitment and enrollment

**Provide a description of the methods which will be used to determine the progress of the study, including periodic assessments of data quality, timelines, recruitment, and enrollment as appropriate:**

Data collected via web-based electronic data collection forms will include internal logic and quality control checks to ensure data is valid at the point of entry. Data errors will need to be updated by the participant before data will be saved. A data analyst will assess all data collected for quality and face validity; data that is perceived to be inaccurate may be excluded from analyses. Our team will create a study timeline at the start of any participant recruitment, and we will review the study's progress including adhering to the timeline biweekly.

Team meetings will assess recruitment, enrollment and study completion rates. A log of those rates will be kept in real time. Research staff will report to the PI any concerns with the study administration.

## 6. Risks & Benefits

Note: Risks may be physical, psychological, social, legal, economic, to reputation, or others.

### a. Describe any potential risks, their likelihood and seriousness:

1. Exposure to Food Allergens: The children will be consuming a standardized meal as well as snack foods. Children with food allergies could experience an allergic reaction to food ingredients
2. Loss of confidentiality: We will collect behavioral and socio-demographic information. Loss of privacy may lead to problems with insurability or social stigmatization

### b. Confirm that risks to subjects have been minimized, by use of procedures which are consistent with sound research design and which do not unnecessarily expose subjects to risk:

1. Exposure to Food Allergens: We will request information about the child's food allergy status multiple times. We will ask the parent if the child has any food allergies during the initial recruitment telephone call and in the written consent form. We will additionally ask both the parent and child whether the child has any food allergies before the child begins his/her participation in the study. Children with relevant food allergies will be excluded from this study to avoid the possibility of an adverse allergic response.
2. Confidentiality: Data collection and analysis will be handled in a confidential manner to protect subject privacy. All electronic data will be stored in a password-protected and encrypted database on a secure Dartmouth server. All paper files will be stored in a locked file cabinet in a secure office. All subject data will be de-identified, and only the primary investigator and research team members who directly contact the participants will have access to the information necessary to link them to their de-identified data. The information collected for this study will be used only for purposes of the research as stated earlier in this form and data will be destroyed when it is no longer needed.

### c. Describe why all the risks to subjects are reasonable in relation to both anticipated benefits and the knowledge expected to be gained from the study:

This study involves minimum risk to participant, and the study findings are to benefit the broader population. Any risks to participants associated with the study are thought to be reasonable.

## 7. Unexpected Events or Incidental Findings

Note: It may be important to consider the potential for certain unanticipated events to occur, for example:

- finding an anomaly in a MRI
- discovering child abuse
- causing distress in interviews of a sensitive nature

### Describe potential events and provide a plan of action:

We do not anticipate any adverse effects. Should any children or parent experience discomfort during the study, he/she will be encouraged to contact the PIs, [name] at [contact], or the Committee for the Protection of Human Subjects at Dartmouth College [contact]. If any participant expresses a desire to learn more about health behaviors for their child, the participant will be directed to relevant material published by the U.S. Centers for Disease Control and Prevention or the USDA.

## 8. Deception

Does any part of this study involve deception or withholding of information from participants?

Yes       No

If Yes, provide an explanation which addresses the following:

- A description of the deception being used
- Why the deception is necessary
- A plan for debriefing, or providing subjects with the pertinent information after participation

We will not completely disclose the purpose of the main study or the purpose of the sub-study to participants in order to avoid bias. This may lead to the participants feeling distressed about being deceived or distrustful of scientific research. In order to address the risks associated with not completely disclosing the research aims of the study, we will send a letter to parents that explains the full purpose of the study when the study is complete. We will explain that we did not reveal the study purpose because we thought that such knowledge might have influenced their children's behavior. We will provide our contact information so that parents and/or their children can discuss the study further if they desire. These procedures will also be followed for the sub-study.

The full debriefing of the main study reveals the objective of the Tetris game, which is to assess how much attention participants pay to the peripheral food cues as they play Tetris. However, because the Tetris game is used for the same purpose in the sub-study, fully debriefing participants after they finish the main study but before they complete the sub-study (as is our current protocol) may affect their responses in the Tetris game during the sub-study. For this reason, those participants in the main study that choose to participate in the sub-study will be debriefed of both studies after they complete the sub-study.

